1 PROTOCOL SUMMARY

1.1 SYNOPSIS

Title: A multi-center, randomized, double blind, parallel-arm, placebo controlled trial of mepolizumab for treatment of adults and adolescents with active eosinophilic esophagitis and dysphagia-predominant symptoms

Study Description: This multi-center, randomized, double blind, parallel-arm, placebo controlled trial will determine whether mepolizumab is more effective than placebo for improving symptoms of dysphagia and decreasing esophageal eosinophil counts in adults and adolescents with active eosinophilic esophagitis after an initial 3-month treatment course and will also assess the impact of an additional 3-months of treatment.

Objectives: Primary Objectives:

1. To determine whether mepolizumab is more effective than placebo for improving symptoms of dysphagia as measured by the validated Eosinophilic Esophagitis Symptom Activity Index (EEsAI) in adults and adolescents with active eosinophilic esophagitis after a 3-month treatment course.
2. To determine whether mepolizumab is more effective than placebo for decreasing esophageal eosinophil counts in adults and adolescents with active eosinophilic esophagitis after a 3-month treatment course.

Secondary Objectives:

1. To determine predictors of symptomatic and histologic response to mepolizumab treatment, including potential biomarkers.
2. To assess durability of symptomatic and histologic response to mepolizumab after 6 months of treatment in patients initially randomized to the active medication (this includes a 3-month blinded second phase of treatment).
3. To assess histologic response to a lower dose of mepolizumab treatment in patients initially randomized to the placebo arm (this will be in a 3-month blinded second phase); symptom response will also be assessed in this phase.
4. To assess safety of mepolizumab over 3 and 6 months of treatment (this includes both 3-month study phases).

Outcomes:

Primary Outcome:

1. Mean change in dysphagia as measured by the EEsAI score (7-day recall) from baseline to 3-months post-treatment.

Secondary Outcomes:

1. Proportion of patients who have clinical remission as defined by an EEsAI score of ≤ 20 .
2. Proportion of patients who have a clinical response, as defined by an EEsAI score decrease of ≥ 20 points.
3. Absolute peak eosinophil count (measured in eos/hpf) after 3-months of treatment.
4. Levels of histologic response after 3-months of treatment including < 15 , ≤ 6 , and ≤ 1 eos/hpf.

[figure not shown]

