3 OBJECTIVES AND OUTCOMES

OBJECTIVES	OUTCOMES	JUSTIFICATION FOR OUTCOMES
To determine whether mepolizumab is more effective than placebo for improving symptoms of dysphagia as measured by the validated Eosinophilic Esophagitis Symptom Activity Index (EEsAI) in adults and adolescents with active eosinophilic esophagitis after a 3-month treatment course.	3-month EEsAI score	The EEsAI is a validated and responsive PRO, developed by an international team of EoE experts, that measures dysphagia frequency, dysphagia severity, and food avoidance/modification behaviors, in patients with EoE. ^{42, 45-47} It has now been used in several clinical trials, ⁴⁸⁻⁵¹ including recently published abstract data emphasizing the responsive nature of this instrument. ^{49, 51}
To determine whether mepolizumab is more effective than placebo for decreasing esophageal eosinophil counts in adults and adolescents with active eosinophilic esophagitis after a 3-month treatment course.	3-month peak eosinophil count	The peak eosinophil count is the currently accepted marker of histologic disease activity.

Please see section 9.4 for full description of outcomes.

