5 STUDY POPULATION

5.1 INCLUSION CRITERIA

In order to be eligible to participate in this study, an individual must meet all of the following criteria:

1. Age 16-75*
2. Diagnosis of EoE as per consensus guidelines (including PPI non-response**).^{2, 43}
3. Active eosinophilia on esophageal biopsy, with a peak count of least 15 eos/hpf from at least one esophageal level.***
4. Biopsies from the stomach and duodenum that have ruled out alternative etiologies in all children and in adults with abnormal endoscopic findings or when other gastric or small intestinal conditions are clinical possibilities. If these samples have been obtained during a previous endoscopic evaluation and in the judgement of the site-Investigator the patient has not had a clinically significant change that would merit repeat gastric/duodenal biopsies, then prior normal gastric and duodenal biopsies are acceptable to exclude alternate etiologies.
5. Active symptoms of dysphagia with more than 3 episodes of dysphagia over a period of 2 weeks during the screening period, and an Eosinophilic Esophagitis Symptom Activity Index (EEsAI; see below for details) score of ≥ 27 at baseline.****
6. Able to read, comprehend, and sign consent form.
7. Have maintained a stable diet for 6 weeks prior to enrollment.*****
8. Able to maintain a stable diet throughout the duration of the study period. *****
9. Female subjects of childbearing potential who have had their first menses agree to use a highly effective method of birth control during the study and for 30 days after the last dose of study drug. Female subjects with reproductive potential who are using systemic contraceptives (e.g., oral contraceptives, injectable contraceptives, implantable/insertable hormonal contraceptive products, or transdermal patches) to prevent pregnancy must have stable use for ≥ 28 days prior to screening. See section 5.3 for additional details.

* The rationale for this criterion is that adolescents and adults with EoE have a very similar clinical presentation with dysphagia-predominant symptoms.²¹ If we were to enroll younger patients there would be few who would meet the dysphagia threshold, and the symptom metric we will use was not validated in younger patients.⁴² Patients of any age can have EoE, but in patients above the age of 75 malignancy is a concern with clinical symptoms of dysphagia, and EoE becomes less common.¹²

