6.3 MEASURES TO MINIMIZE BIAS: RANDOMIZATION AND BLINDING

Subjects will be randomized 1:1 to either mepolizumab or a placebo injection. Randomization will be administered centrally but will be at the level of the site using a blocked randomization protocol with computer-generated variable block sizes. At each site, patients will be categorized as either a prior steroid non-responder or not, and then will be randomized within that categorization. The investigational pharmacy at each site will then receive the randomization information and provide study drugs. Allocation will be concealed from all investigators, subjects, and data analysts. The study monitor will be unblinded to treatment assignments and can escalate issues to the medical monitor who can be unblinded if necessary (e.g. in the event of a safety concern or DSMB request). Of note, we will balance the groups for prior steroid non-response but will not be formally stratifying on this variable for power calculations or analysis purposes. Steroid non-response is defined as greater than 15 eos/hpf after a 2-month course of a swallowed/topical steroid at a standard dose (standard dose = 2mg/d of budesonide or 1760 mcg/d of fluticasone).

This is a double-blind study. Subjects, investigators, endoscopists, nurses, statisticians, and study staff will all be masked as to allocation. To maintain the study blind, only unblinded pharmacist(s) at the investigational pharmacy at each site will dispense study drug. The medication will be mixed by the investigational pharmacy, and only blinded syringes with "study drug" will be provided to use in the study. These will either have the correct active dose of mepolizumab or a matched normal saline placebo. In the first blinded phase, subjects randomized to mepolizumab will receive three injections with active medication, and subjects randomized to placebo will receive three injections with placebo. In the second blinded phase, subjects who were initially randomized to mepolizumab will continue to receive three injections of active medication. However, subjects who were initially randomized to placebo will receive one injection of mepolizumab and 2 injections of placebo.

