8.1.3 SCREENING AND BASELINE ENDOSCOPY WITH BIOPSY AND EREFS

Prior to the screening endoscopy, subjects must be deemed eligible per the EEsAI questionnaire and dysphagia questionnaire. Sites must obtain approval from the lead site prior to completing any screening endoscopies for this study. This is to ensure subjects meet symptom requirements to be eligible for the study.

During the screening endoscopy, esophageal biopsies will be obtained from the following locations:

- Distal esophagus (3-5 cm above the Z-line/squamo-columnar junction)
- Proximal esophagus (~15 cm above the Z line and within 10 cm of the esophageal inlet)

Up to 6 esophageal biopsies will be obtained from each location, focusing on areas of endoscopic abnormalities, if present. Biopsies to determine eligibility will be immediately shipped to a Central Lab for analysis.

Additionally, all children (<18 years of age) will have additional biopsies from the stomach (up to 4: 2 from the antrum and 2 from the gastric body) and duodenum (up to 4) taken to rule out alternative etiologies. Similarly, adults (≥ 18 years of age) with abnormal endoscopic findings or cases where other gastric or small intestinal considerations are clinical possibilities will have biopsies taken from the stomach, duodenum, and/or other targeted areas to rule out alternative etiologies.

Additional details regarding biopsy collection, processing, and shipping instructions can be found in the Manual of Procedures (MOP).

Endoscopic findings will be assessed by each investigator using the EoE Endoscopic Reference Score (EREFS)⁵⁰ in 5 classification categories: fixed rings, exudates, furrows, edema, and stricture.

In addition to obtaining the eosinophil counts required for inclusion in the trial and outcome determination, the esophageal biopsies will be used for evaluation of potential diagnostic and pharmacodynamic markers using appropriate laboratory methodology, including but not limited to other histopathologic findings, immunohistochemistry, and transcript profiling. Samples may also be used for future unspecified studies.

If deemed eligible, then biopsies and EoE Endoscopic Reference Score (EREFS) from the screening EGD will also be used as baseline. For this study, baseline symptoms gathered during the screening visit are used as baseline measurements.

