9.2 SAMPLE SIZE DETERMINATION

The study is powered for the primary outcome, the EEsAI score, which can range from 0-100, with a score of ≤ 20 indicating clinical remission, and a decrease of ≥ 20 points indicating a meaningful clinical response. Based on this, we estimate that with a sample size of 30 patients in each group we would be able to detect a difference in the mean change in EEsAI score of as little of 17, with a power of 0.9 at an α of 0.05, which would allow us to detect the clinically meaningful difference of 20 (see Table). Assuming a 20% dropout rate, we plan to randomize 36 patients in each group.

Table: Sample size considerations

Estimated mean decrease in EEsAI score after 12 weeks of treatment*				
Placebo	Mepolizumab	α	Power	N per group
10	30	0.05	0.9	22
15	30	0.05	0.9	38
20	30	0.05	0.9	85
10	35	0.05	0.9	14
15	35	0.05	0.9	22
15	32	0.05	0.9	30
20	35	0.05	0.9	38
10	40	0.05	0.9	10
15	40	0.05	0.9	14
20	40	0.05	0.9	22

*SD 20 for all

For the secondary outcome of proportion of patients with an EEsAI score ≤ 20 indicating clinical remission, a sample size of 30 in each group would allow us to detect as little as a 40% difference in remission rates between placebo and active therapy with a power of 0.9, a smaller difference that was detected in a recent trial using this metric.⁴⁸ This sample size would also provide ample power the for the absolute eosinophil count and EREFS secondary outcomes.

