9.4 STATISTICAL ANALYSES

9.4.1 GENERAL APPROACH

Descriptive statistics will be used to describe the data. Categorical variables will be presented as proportions and means will be presented with standard deviation and range. If the data are not normally distributed, medians and interquartile ranges will be presented rather than means, and non-parametric testing will be used. For inferential tests, a p value < 0.05 will be considered significant and all tests will be two tailed. All statistical estimates (e.g., medians, proportions, incidence rates, mean differences, correlations, etc.) will be tabulated along with corresponding confidence intervals (CIs).

Interpretation of CIs will play a major role as an integral part of the analysis of the data in concert with any statistical hypothesis tests. To avoid over-reliance on p-values, the magnitudes of estimates and the corresponding confidence intervals will be a focus of the analyses. Reasons for missing data will be investigated and recorded for purposes of statistical analyses. Because of the study design and outcome assessment, primary analyses will require exclusion of participants without outcome data. However, we will perform sensitivity analyses for missing data, initially assigning participants lost to follow up to treatment failure, then assigning them to treatment success and comparing the results, a technique that has been successful in prior clinical trials conducted by our group. For all outcomes, the null hypothesis is that there is no difference between the study groups. All hypothesis tests that are observed to be NOT statistically significant will be reported as being inconclusive.

The study statistician on this study will be [name].

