9.4.3 ANALYSIS OF THE SECONDARY OUTCOMES(S)

Secondary outcomes are as follows:

- The proportion of patients who have clinical remission as defined by an EEsAI score of ≤ 20 . This will be compared between groups by chi-square.

- The proportion of patient who have a clinical response, as defined by an EEsAI score decrease of ≥ 20 points. This will be compared between groups by chi-square.
- The absolute peak eosinophil count (measured in eos/hpf) after 3-months of treatment. Eosinophil counts will be measured by our previously validated protocol, with central reading of all biopsy samples at the lead site to ensure a consistent reading approach.⁴⁹ This will be compared between groups with a two-sample t-test.
- Levels of histologic response after 3-months of treatment including < 15 , ≤ 6 , and ≤ 1 eos/hpf. This will be compared between groups by chi-square.
- Mean change in severity of endoscopic findings as measured by the EoE Endoscopic Reference Score (EREFS) from baseline to 3-months post-treatment. EREFS is a validated and responsive endoscopic severity score that assesses the five most common endoscopic features of EoE: exudates, rings, edema, furrows, and strictures.^{50, 51} This will be compared between the groups using analysis of covariance.
- Mean change in the Straumann Dysphagia Instrument (SDI) from baseline to 3-months post-treatment. The SDI is a direct measure of dysphagia frequency and severity with a 7-day recall period. The score ranges from 0-9, with higher scores indicating more severe dysphagia. This instrument, while not validated, has been shown to be responsive in at least 2 clinical trials.^{23, 49} This will be compared between the groups using analysis of covariance.

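### The month-3 peak eosinophil count is compared without the baseline count already collected; the t-test is valid, so the cost is precision and exposure to chance imbalance, and it may be small

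*Combined protocol and SAP*

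**What the plan says.** The synopsis (1.1) lists as its second primary objective: "To determine whether mepolizumab is more effective than placebo for decreasing esophageal eosinophil counts". Section 3 maps that objective to the "3-month peak eosinophil count". Section 9.4.3 treats this count as a secondary outcome, defined as an absolute level after three months, and says of it: "This will be compared between groups with a two-sample t-test". No covariate is named. The general rule in 9.4.1 applies if normality fails: "If the data are not normally distributed, medians and interquartile ranges will be presented rather than means, and non-parametric testing will be used". That test is not named either, and nothing there brings in baseline.

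A baseline count exists. Section 5.1 requires "Active eosinophilia on esophageal biopsy, with a peak count of least 15 eos/hpf from at least one esophageal level", and 8.1.3 adds: "If deemed eligible, then biopsies and EoE Endoscopic Reference Score (EREFS) from the screening EGD will also be used as baseline".

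Other continuous outcomes are treated differently. EEsAI (9.4.2), EREFS and SDI (9.4.3) and blood eosinophils (9.4.9) are all changes from baseline compared by ANCOVA, though the baseline value is named as covariate only for EEsAI. Section 9.4.9 also applies ANCOVA to the same set of outcomes at month 6, naming no covariate. The optional covariate in 9.4.2 and 9.4.9 is prior steroid response. Section 9.4.5 describes baseline differences but does not adjust for them.

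**The concern.** Where baseline predicts the month-3 count, leaving it out gives a wider confidence interval than the collected data allow. Section 9.4.1 puts estimates and intervals at the centre of interpretation and reports every non-significant result as inconclusive, so avoidable width affects what can be concluded about the second primary objective.

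Randomisation (6.3) balances site and prior steroid response, not the eosinophil count. With about 30 per arm, a chance difference in baseline count passes into the unadjusted comparison in proportion to the baseline correlation. Section 9.2 says that power for this outcome is sufficient but gives no SD, effect size or correlation, so there is no documented margin to absorb the loss.

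**Working it through.** **The plan's own figure.** Section 9.2 sizes the trial on EEsAI "with a sample size of 30 patients in each group": difference 17, SD 20, two-sided α 0.05, power 0.90. The normal formula gives 2 × (1.960 + 1.282)² × 20² / 17² = 29.1, so 30 per group. This reproduces. There is no corresponding figure for the eosinophil count.

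**Validity.** In simulation at 30 per arm with no treatment effect, the unadjusted t-test rejected in 4.8–5.0% of trials with normal data and 3.6–3.9% with log-normal data. Type I error is not inflated.

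**Precision.** Let r be the within-arm correlation of baseline with month 3 among analysed patients. With n = 30 per arm, the ratio of CI width with baseline to width without is about

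√(1 − r²) × √(1 + 1/(2n − 4)) = √(1 − r²) × √(1 + 1/56) = √(1 − r²) × 1.009.

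The second factor is the price of estimating the slope.

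The simulation assumed rounded log-normal counts with median 60, the entry floor of 15, log-SD 0.8 to 1.4 and 30 per arm. Each ratio compares the same scale with and without baseline, so a change of scale contributes nothing. Correlations were set before applying the floor; the floor lowers them among enrolled patients.

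| Correlation set, both arms | r among enrolled | Formula | Simulated, log(count+1) | Simulated, ranks |
|---|---|---|---|---|
| 0 | 0 | 1.009 | about 1.01 | – |
| 0.2 | 0.16–0.18 | 0.992–0.996 | 0.99–1.00 | 0.99–1.00 |
| 0.4 | 0.33–0.37 | 0.937–0.952 | 0.94–0.95 | 0.94–0.96 |
| 0.6 | 0.51–0.56 | 0.836–0.868 | 0.83–0.87 | 0.85–0.88 |

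Formula and simulation agree. In sample-size terms, ignoring the small slope cost, r = 0.5 among analysed patients is worth 30 / (1 − 0.25) = 40 per arm unadjusted.

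**Less favourable cases** (log scale; correlations as set before the floor):

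- 0.4 on placebo, 0.1 on active: 0.98–0.99.
- 0.4 in both arms, 20% zeros on active: 0.97–0.99.
- 0.4 and 0.1, with 20% zeros on active: 0.99–1.00.
- 0.6 and 0.2, with 20% zeros on active: 0.97–0.99.
- 0.6 in both arms, 20% zeros on active: 0.92–0.97.

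Active-arm falls of 7%, 55% or 80% moved the ratios by at most 0.02. Null rejection was 0.047–0.060 for log-scale ANCOVA and 0.046–0.059 for rank ANCOVA.

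**Chance imbalance.** The difference between arms in mean log baseline has standard error √(2/30) = 0.258 SD. The probability that it exceeds 0.5 SD either way is 2 × [1 − Φ(0.5/0.258)] = 0.053. At exactly 0.5 SD, the simulated unadjusted ratio of month-3 counts is off by a factor of 1.07–1.12, 1.15–1.24 and 1.24–1.39 at set correlations of 0.2, 0.4 and 0.6. It is off by less if the active-arm correlation is weaker.

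**The case against.** The strongest reply is that this is no error. The outcome is declared as a level, not a change; a t-test on a level is coherent and valid; and the outcome is secondary. All of that stands, and it limits the point to efficiency. It does not argue against adjustment, because a month-3 level can be regressed on baseline without changing what is measured.

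Second, the size rests wholly on assumptions, and the top of the range needs a strong correlation in both arms. The protocol expects the drug to lower tissue eosinophils and sets response thresholds as low as 1 eos/hpf, so low counts on active treatment are plausible and the gain may be close to nothing. That also stands.

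Third, the imbalance argument is not wholly separate. Averaged over randomisations, the t-test interval already allows for baseline imbalance; the shifts above apply given an imbalance actually seen, and one beyond 0.5 SD occurs in about 5% of trials. This is fair: the two costs overlap and should not be added.

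Fourth, the scale of analysis may matter more than the covariate. In one log-normal simulation (log-SD 1.2, effect 0.72 SD on the log scale), power was about 53% for the raw t-test and 76% for a rank test. Log-scale ANCOVA gave 80% at correlation 0.2 and 89% at 0.5. The fallback in 9.4.1 recovers part of that. The gain from scale is separate from the gain claimed here, and the log scale does change the effect measure to a ratio.

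**Conclusion.** The concern holds as a point to consider. The planned comparison omits a baseline value that the trial already collects. It is valid and unbiased over randomisations; what is lost is precision and protection against a chance imbalance.

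Under the stated assumptions the interval would narrow by 0 to 17% when the correlation is 0.2 to 0.6 in both arms. Where the correlation is weaker on active treatment, or is 0.4 with 20% zeros on active, the gain is 0 to 3%; at 0.6 in both arms with those zeros it is 3 to 8%. If baseline carries no information, the interval is about 1% wider. The median, SD, correlations and share of zeros are all assumed. The case for change rests on the asymmetry between a possible loss of about 1% and a possible gain of up to 17%. No claim is made about power for this outcome, since the plan gives no effect size or SD for it.

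**What to change.** Before unblinding, replace the t-test for this outcome in 9.4.3 with an ANCOVA of the month-3 peak count on treatment and baseline peak count, on a scale fixed in advance. One option is log(count+1), reported as a ratio of geometric means of count+1 with a 95% CI, alongside raw medians by arm. Name a rank-based ANCOVA on baseline as the sensitivity analysis, in place of the data-triggered fallback for this outcome.

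Handle prior steroid response as in the primary analysis, once the plan is made consistent: 6.3 says the trial "will not be formally stratifying on this variable for power calculations or analysis purposes", while 9.4.2 and 9.4.9 allow it as a covariate.

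The cost is one or two sentences, with no new data for patients who have a screening endoscopy. There are three downsides. The effect becomes a ratio that depends on the added constant when counts are near zero. The interval widens by about 1% if baseline is uninformative. Footnote 2 to the schedule in 1.3 may allow a historical endoscopy in place of the screening one, and 9.4.3 does not say whether central reading covers those biopsies. The plan must state how such baseline counts enter the model.
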